6.3.1 Potential drug-induced liver injury IMP discontinuation criteria

Subjects with potential drug-induced liver injury must be assessed to determine if IMP must be discontinued. In addition, all concomitant medications and herbal supplements that are not medically necessary should also be discontinued.

The PDILI criteria below require immediate and permanent discontinuation of IMP:

- Subjects with either of the following:
 - ALT or AST $\geq 5xULN$
 - ALT or AST $\geq 3xULN$ and coexisting total bilirubin $\geq 2xULN$

The PDILI criterion below requires immediate discontinuation of IMP:

- Subjects with ALT or AST $\geq 3xULN$ who exhibit temporally associated symptoms of hepatitis or hypersensitivity. Hepatitis symptoms include fatigue, nausea, vomiting, right upper quadrant pain or tenderness. Hypersensitivity symptoms include fever (without clear alternative cause), rash, or eosinophilia (ie, $>5\%$).

The PDILI criterion below allows for subjects to continue on IMP at the discretion of the investigator.

- Subjects with ALT or AST $\geq 3 \times \text{ULN}$ (and $\geq 2 \times$ Baseline) and $< 5 \times \text{ULN}$, total bilirubin $< 2 \times \text{ULN}$, and no eosinophilia (ie, $\leq 5\%$), with no fever, rash, or symptoms of hepatitis (eg, fatigue, nausea, vomiting, right upper quadrant pain or tenderness).

Evaluation of PDILI must be initiated as described in [Section 11.6.1](#). If subjects are unable to comply with the applicable monitoring schedule, IMP must be discontinued immediately.

Investigators should attempt to obtain information on subjects in the case of IMP discontinuation to complete the final evaluation. Subjects with PDILI should not be withdrawn from the study until investigation and monitoring are complete. All results of these evaluations and observations, as well as the reason(s) for IMP discontinuation and subject withdrawal (if applicable), must be recorded in the source documents. The eCRF must document the primary reason for IMP discontinuation.

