A 12-day blinded Transition Period will be required for eligible subjects who complete the Maintenance Period and who plan to enter EP0034. For subjects randomized to LCM, the Maintenance Period dose will be maintained during the Transition Period. Subjects randomized to PBO will be transitioned in a double-blind fashion as described in [Table 7-2](#).

Taper Period

A blinded Taper Period (8 to 16 days, depending on dose level achieved) will be required for subjects who discontinue study medication prematurely and for subjects who complete the Maintenance Period but will not be entering EP0034. Study medication will be tapered as described in [Table 7-3](#).

At the discretion of the investigator, AEDs may be added or adjusted and VNS adjustments may be made once the subject enters the Taper Period.

Safety Follow-Up Period

There will be a 30-day Safety Follow-Up Period for subjects not entering the open-label extension study (EP0034). The Safety Follow-Up Period will include a Safety Follow-Up Clinic Visit 14 days (± 2 days) after the final dose of study medication, and a Safety Follow-Up Telephone Contact 30 days (-1/+3 days) after the final dose of study medication.

Unscheduled visits can be conducted at the discretion of the investigator.

Detailed schedules of study procedures are provided in [Section 5.2](#), and study schematic diagrams are included in [Section 5.3](#).

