Investigators should attempt to obtain information for subjects who withdraw. For subjects considered as lost to follow up, the investigator should make an effort (at least 1 phone call and 1 written message to the parent[s] or legal representative[s]/caregiver[s]), and document his/her effort (date and summary of the phone call and copy of the written message in the source documents), to complete the final evaluation. All results of these evaluations and observations, together with a narrative description of the reason(s) for removing the subject, must be recorded in the source documents. The eCRF must document the primary reason for withdrawal.

Investigators should contact the Medical Monitor, whenever possible, to discuss the withdrawal of a subject in advance.

Subjects withdrawn from the study will proceed to the blinded Taper Period described in Section 7.2.4 and the assessments described in Table 5-3 will be performed.

Subjects who are withdrawn from the study will not be replaced.

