7.2.4 Taper Period

Subjects who are not eligible for or who choose not to enter EP0034, or subjects who do not complete the Maintenance Period, will proceed to a blinded Taper Period of 8 to 16 days during which treatment with study medication will be withdrawn. The taper steps will be based on the dose of LCM (or matching PBO) achieved during the Maintenance Period according to Table 7-3. A slower taper is permitted if medically necessary. In case of an emergency, a faster taper is permitted after discussion with the Medical Monitor, whenever possible.

Subjects who are withdrawn during either the Titration Period or the Transition Period will also proceed to the Taper Period, and study medication will be tapered starting at the respective dose achieved during the Titration Period or the Transition Period. At the discretion of the investigator, AEDs may be added or adjusted and VNS adjustments may be made once the subject enters the Taper Period.

Table 7-3: Dosing of LCM (or matching PBO) during the Taper Period

LCM (or matching PBO) dose achieved	LCM (or matching PBO) doses for the Taper Period			
	Day 28 to Day 31	Day 32 to Day 35	Day 36 to Day 39	Day 40 to Day 43
11 or 12mg/kg/day	9mg/kg/day	6mg/kg/day	4mg/kg/day	2mg/kg/day
9 or 10mg/kg/day	8mg/kg/day	6mg/kg/day	4mg/kg/day	2mg/kg/day
7 or 8mg/kg/day	6mg/kg/day	4mg/kg/day	2mg/kg/day	2mg/kg/day
5 or 6mg/kg/day	4mg/kg/day	2mg/kg/day	2mg/kg/day	NA
4mg/kg/day	2mg/kg/day	2mg/kg/day	NA	NA

LCM=lacosamide; NA=not applicable; PBO=placebo

Note: The study day numbers provided are for subjects who complete the Maintenance Period and enter the Taper Period. The study day numbers provided do not apply to subjects who enter the Taper Period at other times.

Subjects who enter the Taper Period will return for the Taper Visit at the end of the Taper Period.

Taper of LCM may not be required for some subjects who are on the lowest dose of study medication or who need to discontinue study medication abruptly, depending on the treatment option selected by the investigator in consultation with the medical monitor.

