8.4.3 Transition Period: Transition Visit 2 (Day 40)

Transition Visit 2 will also serve as Visit 1 for EP0034.

During Transition Visit 2, the following assessments will be performed:

- Concomitant medications
- Concomitant AEDs
- VNS assessment (if applicable)
- Physical examination (complete)
- Vital signs (BP and pulse rate, including orthostatic assessments where feasible according to investigator judgment)
- Body weight
- Neurological examination (complete)
- 12-lead ECG (2 interpretable recordings [approximately 20 to 30 minutes apart] to be performed prior to any blood draws and vital signs assessment and, if possible, with the subject in a supine position for 5 minutes preceding ECG recording)
- Blood sample for clinical chemistry/hematology
- Contact IXRS
- Return study medication
- AE reporting
- Review withdrawal criteria

8.5 Taper Period: Telephone Contact 4 (Day 32) and Taper Visit (Day 36, Day 40, or Day 44)

A blinded Taper Period (8 to 16 days, depending on the dose level achieved) will be required for subjects who discontinue study medication prematurely and for subjects who complete the Maintenance Period but will not enroll in EP0034. Study medication will be tapered as described in [Table 7-3](#).

During the Taper Period, a telephone contact will be conducted on Day 32 and a Taper Visit will be scheduled at the end of the Taper Period, on Day 36, 40, or 44. Note that the study day numbers provided are for subjects who complete the Maintenance Period and enter the Taper Period; the study day numbers provided do not apply to subjects who enter the Taper Period at other times.

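### The liver stopping rules require study drug to stop at once, but Protocol 5.1 and 8.5 require an 8 to 16 day taper on it after any premature stop, and 7.2.4 waives that taper only at discretion

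*Protocol*

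**What the plan says.** **The stop.** Protocol 6.3.1 sets two criteria (ALT or AST at 5 times ULN or above; or 3 times ULN or above with total bilirubin at 2 times ULN or above) under the sentence "The PDILI criteria below require immediate and permanent discontinuation of IMP". For transaminases at 3 times ULN or above with symptoms of hepatitis or hypersensitivity it says "The PDILI criterion below requires immediate discontinuation of IMP". Table 11-3 gives the same actions. Neither place mentions a taper.

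**The taper.** Section 5.1 states: "A blinded Taper Period (8 to 16 days, depending on dose level achieved) will be required for subjects who discontinue study medication prematurely". Section 8.5 repeats it: "A blinded Taper Period (8 to 16 days, depending on the dose level achieved) will be required for subjects who discontinue study medication prematurely". Section 7.2.4 sends the same children to the taper ("or subjects who do not complete the Maintenance Period, will proceed to a blinded Taper Period of 8 to 16 days"), and Section 6.3 adds "Subjects withdrawn from the study will proceed to the blinded Taper Period described in Section 7.2.4". The taper is given on study medication, as its dosing table shows: "Table 7-3: Dosing of LCM (or matching PBO) during the Taper Period".

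**The relief.** Section 7.2.4 allows a faster taper in an emergency. It also says "Taper of LCM may not be required for some subjects who are on the lowest dose of study medication", and extends this to children who have to stop abruptly, depending on the option that the investigator picks in consultation with the medical monitor. It does not mention liver injury or 6.3.1.

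**Related text.** Section 6.3.1 holds back study withdrawal for liver cases until their work-up and follow-up have finished. Section 11.6.1 forbids rechallenge with a substance that may have caused liver injury.

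**The concern.** A child who meets a liver stopping criterion is also a child who has stopped study medication prematurely. One part of the protocol then says that the drug stops now. Another says that a further 8 to 16 days of it are required. The only bridge between them is permissive and does not name the case it would have to cover, so a site reading 7.2.4 could take an obligatory stop for a matter of choice.

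Two things are at stake. The first is exposure to study drug after a safety stop. The second is the date of the last dose. It anchors the 30-day treatment-emergent window (Protocol 13.2.1, SAP 10.2), the Safety Follow-Up visits (Protocol 5.1) and the start of the Safety Follow-Up Period (SAP 3.2.2). It would depend on which section a site followed, in the very children whose liver events matter most.

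**Working it through.** **Step 1. The passages side by side, for one child meeting a liver criterion**

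- 6.3.1 and Table 11-3: immediate stop of study drug. It is permanent for two criteria; for the symptomatic criterion Table 11-3 allows a temporary or permanent stop.
- 5.1 and 8.5: taper required after premature discontinuation, with no exception. This conflicts at once.
- 7.2.4: taper by default, with a discretionary exception for abrupt stops. A site can comply with 6.3.1 through it, but is not told to.
- 6.3: applies at study withdrawal, which 6.3.1 defers. The conflict is therefore secondary and comes later. Read literally, the sentence would then send a child already off drug to a dosed taper, against the no-rechallenge statement in 11.6.1.

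**Step 2. Reproduce the protocol's taper length.** Input: Table 7-3, in 4-day steps. Days = number of dosed steps x 4. This gives 2 x 4 = 8, 3 x 4 = 12 and 4 x 4 = 16 days, which matches the stated 8 to 16. After Maintenance ends on Day 27, the Taper Visit falls on Day 27 + days + 1 = 36, 40 or 44, as the protocol states.

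**Step 3. Drug given after the stop, if 5.1 and 8.5 were followed.** Amount = 4 x (sum of the daily doses in the row), for a child receiving lacosamide:

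| Dose achieved (mg/kg/day) | Calculation | mg/kg | Days |
|---|---|---|---|
| 11 or 12 | 4 x (9+6+4+2) | 84 | 16 |
| 9 or 10 | 4 x (8+6+4+2) | 80 | 16 |
| 7 or 8 | 4 x (6+4+2+2) | 56 | 16 |
| 5 or 6 | 4 x (4+2+2) | 32 | 12 |
| 4 | 4 x (2+2) | 16 | 8 |

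Under 6.3.1 the amount is 0. Every Maintenance dose (8 to 12 mg/kg/day) falls in a 16-day row. From 12 mg/kg/day, 84/12 = 7 full days at the dose being stopped; from 8 mg/kg/day, 56/8 = 7.

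A placebo child tapered from Titration or Maintenance receives matching placebo, so 0 mg/kg. A placebo child stopped during Transition is already on lacosamide at 4, 6 or 8 mg/kg/day (Table 7-2), so the rows giving 16, 32 or 56 mg/kg apply.

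**Step 4. Shift in the last-dose anchor.** Let D be the day of the liver stop. With no taper, the treatment-emergent window closes at D + 30. With a 16-day taper it closes at D + 16 + 30 = D + 46. The Safety Follow-Up Clinic Visit target moves from D + 14 to D + 16 + 14 = D + 30.

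**The case against.** The strongest reply is that the texts can be applied together. Section 7.2.4 expressly provides for children who need to stop abruptly, with the medical monitor consulted. Section 11.6.1.1 already requires that the Medical Monitor be notified of every liver event within 24 hours and that the child be discussed as soon as possible. The same person is thus involved in both decisions, and a careful investigator would probably let the specific liver rule prevail. This stands as a reason why sites are less likely to diverge. It does not remove the conflict: 5.1 and 8.5 remain unqualified, and the exception is optional and does not name 6.3.1. Both 6.3.1 and the abrupt-stop sentence came in with Amendment 2, but the reasons given there for that sentence are a switch to another antiepileptic drug and stopping from 2 mg/kg/day, not liver injury.

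A reader might also infer more than the text supports:

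- *That 6.3 competes with 6.3.1 on the day of the stop.* It does not. It governs study withdrawal, which 6.3.1 defers, and by pointing to 7.2.4 it brings in the exception there.
- *That every affected child would get more than two weeks of lacosamide.* That holds only for the 16-day rows and only for children receiving lacosamide, and it ignores the faster taper allowed in an emergency.
- *That the lowest-dose wording in 7.2.4 contradicts the 8-day taper at 4 mg/kg/day.* It does not: this is a default with a stated exception.
- *That the safety tables as a whole become unreliable.* The SAP uses the actual last dose, so its rules work on either path. The main adverse-event tables cover the Treatment Period, which normally ends at Visit 6 or the early termination visit (SAP 3.2.2). Only the windows tied to the last dose, and the Taper, Safety Follow-Up and overall tables, could move.

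**Conclusion.** The point holds as an inconsistency in a safety rule. Sections 6.3.1 and Table 11-3 mandate an immediate stop. Sections 5.1 and 8.5 mandate a dosed taper for the same event. Section 7.2.4 offers a way out only by discretion, and the later wording in 6.3 is a secondary conflict with 11.6.1.

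If 5.1 and 8.5 were followed, a child in the lacosamide arm would receive 16 to 84 mg/kg over 8 to 16 days after the stop, and the last-dose date would move by up to 16 days. These figures assume the default Table 7-3 schedule, without the slower or faster taper that 7.2.4 permits. The documents give no expected count of liver stops, so the number of children affected is unknown; it is likely to be small. The efficacy analysis, sample size, power and alpha are unaffected. It should be corrected because it concerns a mandatory safety stop and the correction is cheap.

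**What to change.** Reconcile 5.1, 8.5, 7.2.4 and 6.3 with 6.3.1, Table 11-3 and 11.6.1. Each taper passage should state explicitly, and in identical words, whether the taper applies to children whose study drug is stopped under 6.3.1, with a cross-reference to that section. The wording in 6.3 should also say what happens when a child already off drug for a liver event is later withdrawn from the study. Which rule applies is a decision for the sponsor's medical team.

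The cost is wording in the next protocol amendment and a letter to sites. No visits or patients are added, and the SAP needs no change because it already works from the actual last dose.

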7 STUDY TREATMENTS

7.1 Description of investigational medicinal products

Investigational medicinal product will be provided as LCM oral solution (LCM 10mg/mL) and matching PBO. The LCM 10mg/mL oral solution and matching PBO oral solution are colorless to pale yellow in appearance. Both oral solutions will be packaged in amber polyethylene terephthalate (PET) bottles.

Study medication will be measured and administered via a dosing syringe. If a subject is unable to swallow the oral solution, administration by feeding tube will be permitted.

It should be noted, in cases of incomplete doses (eg, subject spits out all or a portion of the syrup), missed doses, or administration of an erroneous volume of syrup, study medication should not be readministered.

7.2 Treatment(s) to be administered

At Visit 3, subjects will be randomized in a double-blind manner to 1 of 2 parallel treatment arms: LCM or PBO in a 1:1 ratio. Randomization will occur after completion of the End-of-Baseline video-EEG and after confirmation that the subject has met selection criteria. Randomization will be stratified by age category (≥ 1 month to < 6 months of age, ≥ 6 months to < 1 year of age, ≥ 1 year to < 2 years of age, and ≥ 2 years to < 4 years of age).

At the end of Visit 3, subjects should take the first dose of study medication while in the clinic. At each subsequent clinic visit, subjects should take study medication (and any concomitant AEDs) at the regular time(s). Study medication will be administered orally bid (at approximately 12-hour intervals in the morning and in the evening).

SP0967 will target Maintenance Period doses of LCM 8mg/kg/day to 12mg/kg/day or matching PBO.

7.2.1 Titration Period

Subjects will be dispensed study medication and will begin treatment with LCM oral solution at a dose of LCM 4mg/kg/day or matching PBO. [Table 7-1](#) provides the recommended LCM (or matching PBO) dosing schedule during the Titration Period for subjects to reach the target doses for the Maintenance Period.

Table 7–1: Recommended dosing schedule for LCM (or matching PBO) during the Titration Period

Target LCM (or matching PBO) doses for the Titration Period				
Day 1 to Day 4	Day 5 to Day 8	Day 9 to Day 12	Day 13 to Day 16	Day 17 to Day 20
4mg/kg/day	6mg/kg/day	8mg/kg/day	10mg/kg/day	12mg/kg/day

LCM=lacosamide; PBO=placebo

Dosing flexibility during the Titration Period based on tolerability is allowed in SP0967. After completion of Day 4, investigators will assess whether a subject would tolerate a further dose increase or whether a subject should hold the dose for a longer duration. In addition to holds, subjects may have the study medication titrated to a higher dose or back titrated by LCM 1mg/kg/day or 2mg/kg/day (or matching PBO) steps. If study medication is titrated to a higher dose, the subject should remain on the higher dose for ≥ 4 days unless a back-titration step based on tolerability is required.

If study medication is back titrated, the back titrated dose must never be lower than LCM 4mg/kg/day (or matching PBO) and be maintained for ≥ 3 days before a subsequent dose increase. After study medication is back titrated, if a subject returns to a higher dose previously administered, the dose must be maintained for ≥ 3 days (in order to reach steady state) before subsequent titration to a higher dose. After study medication is back titrated, if a subject subsequently receives a higher dose not previously administered, that dose should be maintained for ≥ 4 days unless tolerability concerns require a back titration.

There is no limit to the number of titration steps or dose holds allowed and all are at the investigator's discretion; however, subjects must achieve at least the minimum target dose of study medication (LCM 8mg/kg/day or matching PBO) for the final 3 days of the Titration Period. If it becomes apparent that the subject will not be able to reach the minimum target dose, then the subject should be withdrawn from the Titration Period and enter the Taper Period.

No adjustments in dose of study medication will be permitted after Day 20. Subjects who are not able to tolerate the study medication at an earlier time point during the Titration Period or who are not able to tolerate the reduced dose at the end of the Titration Period will be withdrawn from the study and enter the blinded Taper Period. Subjects who withdraw during the Transition Period will also enter the blinded Taper Period.

7.2.2 Maintenance Period

Subjects who achieve at least the minimum target dose of study medication (LCM 8mg/kg/day or matching PBO) for the final 3 days of the Titration Period will enter the 7-day blinded Maintenance Period on the dose achieved at the end of the Titration Period and will continue to receive this dose for the duration of the Maintenance Period. No adjustments to study medication dose will be allowed during the Maintenance Period.

Subjects who complete the Maintenance Period will be offered the opportunity to enroll in an open-label extension study (EP0034). Eligible subjects who choose to enroll in EP0034 will proceed to a blinded 12-day Transition Period.

7.2.3 Transition Period

During the Transition Period, subjects randomized to PBO will be transitioned in a double-blind manner from PBO to LCM 8mg/kg/day over a 12-day period. Transition dosing will be administered according to Table 7-2. Subjects randomized to LCM will remain on their Maintenance Period dose during the Transition Period.

Table 7-2: Transition Period LCM dosing schedule for subjects randomized to PBO

Maintenance Period	LCM doses for the Transition Period		
	Day 28 to Day 31	Day 32 to Day 35	Day 36 to 39
PBO	4mg/kg/day	6mg/kg/day	8mg/kg/day

LCM=lacosamide; PBO=placebo

At Visit 1 of EP0034, all subjects will transition to a dose of LCM 10mg/kg/day. The SP0967 final Transition Visit is the same as Visit 1 of EP0034.

7.2.4 Taper Period

Subjects who are not eligible for or who choose not to enter EP0034, or subjects who do not complete the Maintenance Period, will proceed to a blinded Taper Period of 8 to 16 days during which treatment with study medication will be withdrawn. The taper steps will be based on the dose of LCM (or matching PBO) achieved during the Maintenance Period according to Table 7-3. A slower taper is permitted if medically necessary. In case of an emergency, a faster taper is permitted after discussion with the Medical Monitor, whenever possible.

Subjects who are withdrawn during either the Titration Period or the Transition Period will also proceed to the Taper Period, and study medication will be tapered starting at the respective dose achieved during the Titration Period or the Transition Period. At the discretion of the investigator, AEDs may be added or adjusted and VNS adjustments may be made once the subject enters the Taper Period.

Table 7-3: Dosing of LCM (or matching PBO) during the Taper Period

LCM (or matching PBO) dose achieved	LCM (or matching PBO) doses for the Taper Period			
	Day 28 to Day 31	Day 32 to Day 35	Day 36 to Day 39	Day 40 to Day 43
11 or 12mg/kg/day	9mg/kg/day	6mg/kg/day	4mg/kg/day	2mg/kg/day
9 or 10mg/kg/day	8mg/kg/day	6mg/kg/day	4mg/kg/day	2mg/kg/day
7 or 8mg/kg/day	6mg/kg/day	4mg/kg/day	2mg/kg/day	2mg/kg/day
5 or 6mg/kg/day	4mg/kg/day	2mg/kg/day	2mg/kg/day	NA
4mg/kg/day	2mg/kg/day	2mg/kg/day	NA	NA

LCM=lacosamide; NA=not applicable; PBO=placebo

Note: The study day numbers provided are for subjects who complete the Maintenance Period and enter the Taper Period. The study day numbers provided do not apply to subjects who enter the Taper Period at other times.

Subjects who enter the Taper Period will return for the Taper Visit at the end of the Taper Period.

Taper of LCM may not be required for some subjects who are on the lowest dose of study medication or who need to discontinue study medication abruptly, depending on the treatment option selected by the investigator in consultation with the medical monitor.

